8.4	Clinical Laboratory Evaluations	22
8.5	Other Safety Measures.....	23
	Appendix 1: List of Planned Figures and Tables.....	23
9	References.....	25

List of Abbreviations

AE(s)	Adverse event(s)
ALT	Alanine aminotransferase
ANA	Antinuclear antibodies
AST	Aspartate aminotransferase
BCG	Bacillus Calmette–Guérin
CBC	Complete blood count
CI	Confidence interval
CIS	Carcinoma in situ
CRF	Case report form
CT	Computed tomography
CTCAE	Common Terminology Criteria for Adverse Events
CTL	Cytotoxic T lymphocytes
CTLA4	Cytotoxic T-lymphocyte associated antigen 4
DFS	Disease free survival
ECG	Electrocardiograms
ECOG	Eastern Cooperative Oncology Group
EGFR	Epidermal growth factor
ELISA	Enzyme-linked immunosorbent assay
ELISPOT	Enzyme-linked immunosorbent spot
EOT	End of Treatment
FDA	Food and Drug Administration
GCP	Good Clinical Practice
gzB	Granzyme B
HR	Hazard Ratio
HLA	Human leukocyte antigen
HIV	Human immunodeficiency virus
IEC	Independent ethics committee
IHC	Immunohistochemistry
IBC	Institutional biosafety committee
ICS	Intracellular cytokine staining
IHC	Immunohistochemistry
IR	Immunologic Response
IRB	Institutional Review Board
ISR	Injection Site Reaction
ITT	Intention to treat
i.v.	Intravenous
IXRS	Interactive Response System
LTFU	Long-term Follow-up
MedRA	Medical Dictionary for Regulatory Activities
MRI	Magnetic resonance imaging
95%CI	95% confidence interval
OR	Odds ratio
OS	Overall Survival
PBMC	Peripheral blood mononuclear cell

PCR	Polymerase Chain Reaction
PD	Progressive Disease
RBC	Red blood cell
RECIST	Response evaluation criteria for solid tumours
SAE	Serious adverse event
SAP	Statistical analysis plan
SD	Standard Deviation OR Stable Disease
SAR	Suspected adverse reaction
SOA	Schedule of Assessments
SOE	Schedule of events
SOC	Standard of care
TCR	T-cell receptor
TURBT	Transurethral resection of bladder tumor
ULN	Upper limits of normal
TCR	T-cell Receptor
TEAE	Treatment emergent adverse event
TIL	Tumor Infiltrating Lymphocyte
TKI	Tyrosine Kinase Inhibitor
ULN	Upper limit of normal
US	United States
WBC	White blood cell

1. Introduction

1.1 Preface

Bladder cancer is the 6th most common cancer in the United States with an estimated 74,690 patients diagnosed in 2014 and 15,580 deaths.¹ Approximately 70-80% of patients have non-muscle invasive bladder cancer (NMIBC) at the time of diagnosis.^{2,3} Transurethral resection of bladder tumour (TURBT) is the standard treatment for NMIBC and aids in the proper diagnosis and staging of disease. Patients with low-risk disease (solitary, primary low-grade, Ta tumours) have high recurrence-free and progression-free rates and an overall favorable prognosis.⁴ In contrast, patients with high-risk disease (T1 and/or high grade and/or *carcinoma in situ (CIS)*) determined at the time of initial resection have a one year recurrence-free rate of approximately 39%.³

Between these two extremes are a large group of patients classified as having intermediate-risk disease, which is defined as multiple or recurrent low-grade Ta tumors.⁴ Since this is a very broad spectrum of patients, the intermediate-risk category can be further stratified. Intermediate-risk patients with at least 3 of the following 4 risk factors – multiple tumours, tumour size > 3cm, early recurrence (<1 year from previous TURBT), or frequent recurrences (i.e. recurrence with a frequency of more than once in any 12-month period) – have treatment regimens and outcomes similar to high-risk patients, with recurrence-free rates of 62% at 1 year and 38% at 5 years resectively.^{3,5} Patients with either high or intermediate-risk disease with 3 or more risk factors will make up the patient population for this protocol.

Adjuvant treatment options for patients with urinary bladder cancer are limited, as systemic chemotherapy appears largely ineffective in this setting.^{6,7} Adjuvant intravesical mitomycin-C and bacillus Calmette-Guérin (BCG) have been used successfully to reduce local recurrence of NMIBC for over 30 years, but nearly a quarter of high-risk patients have evidence of disease 6 months after induction BCG.⁸ Patients with intermediate- or high-risk disease benefit most when induction BCG is combined with a maintenance phase lasting for at least 1 year.^{9,10} However, nearly 15% of these patients will still go on to experience a recurrence after 3 years.¹⁰ Reasons for failure are not well defined, but may be related to toxicities associated with these agents resulting in utilization of intravesical therapy well below recommended dose intensities.^{11,12}

Given the limited long term disease control possible with currently available adjuvant strategies in patients with high risk NMIBC and the progressively less effective and more debilitating outcomes of subsequent rounds of surgical resection, there is a pressing need for alternate or complementary adjuvant strategies, such as vaccine-based immunotherapy, to reduce recurrence and improve tolerability of treatments in this patient group. Immunotherapy with vaccines and checkpoint inhibitors has demonstrated clinical benefit and a survival prolongation in several stage solid tumours such as prostate cancer and metastatic melanoma.^{13,14}

Vesigenurtacel-L is an allogeneic cellular immunotherapy designed to induce cell-mediated immunity and intended for use in treatment of non-muscle invasive bladder cancer (NMIBC). The active ingredient in vesigenurtacel-L is an engineered cell line derived from a human urothelial cancer cell line, UM-UC3, and has been modified to express a secreted gp96-Ig fusion protein. The secreted gp96 acts as a chaperone and adjuvant to induce cellular immune responses to various tumor antigens

expressed by the host cell. The expression plasmid encoding the gp96-Ig fusion protein lacks any sequences known to be capable of mediating integration into mammalian genomes.

After the expansion of cells using current good manufacturing practices (cGMP) the cells are irradiated to render them replication incompetent while maintaining biological activity, including the expression of secreted gp96 and associated tumor antigens.

1.2 Purpose of the analyses

These analyses will assess the efficacy and safety of HS-410 as monotherapy and in combination with BCG in patients with non-muscle invasive bladder cancer who have undergone TURBT.

2 Study Objectives and Endpoints

2.1 Study Objectives

Primary Objective

- **Phase 1:** To characterize the safety and tolerability of monotherapy vaccination with HS-410 in patients with non-muscle invasive bladder cancer.
- **Phase 2:**
 - Arms 1, 2, and 3: To evaluate 1-year disease-free survival in patients with non-muscle invasive bladder cancer treated with BCG in combination with blinded study product (one of two doses of vesigenurtacel-L or placebo).
 - Arm 4: To evaluate 1-year disease-free survival in patients with non-muscle invasive bladder cancer treated with high dose vesigenurtacel-L monotherapy.

Secondary Objectives

Both Phases:

- To evaluate the proportion of patients with recurrence at 3, 6, 12, 18, and 24 months
- To evaluate the proportion of patients with progressive disease at 3, 6, 12, 18, and 24 months
- To evaluate overall disease-free survival
- To evaluate overall survival (OS)
- To evaluate the proportion of patients undergoing post-treatment TURBT or fulguration by 12 and 24 months
- To evaluate the proportion of patients undergoing cystectomy by 12 and 24 months
- To evaluate the proportion of patients with immunologic response of PBMCs via intracellular cytokine staining (ICS) by flow cytometry and/or ELISPOT on CD8+ cells following vesigenurtacel-L vaccination

Phase 2 only:

- To evaluate the safety of the combination of vesigenurtacel-L and BCG
- To evaluate the safety of high dose vesigenurtacel-L monotherapy

Primary Endpoint

- **Phase 1:** Safety and tolerability of monotherapy vaccination with HS-410 in patients with non-muscle invasive bladder cancer.
- **Phase 2:** 1-year disease-free survival in patients with non-muscle invasive bladder cancer treated with BCG in combination with one of two doses of HS-410 or placebo, or with high dose HS-410 without BCG. The 1-year disease-free survival rate is defined as the proportion of patients who are alive and free from recurrence and progression at 12 months following randomization.

Secondary efficacy endpoints:

Both Phases:

- Proportion of patients with recurrence at 3, 6, 12, 18, and 24 months from randomization, estimated based on Kaplan-Meier curves. Recurrence is defined as disease that has recurred to the same extent of disease (ie same stage / severity) or to a lower stage/severity of disease compared to screening.
- Proportion of patients with progressive disease at 3, 6, 12, 18, and 24 months from randomization. Progressive disease is defined as an increase in T stage from TIS or Ta (at screening) to T1 (lamina propria invasion), development of T2 or greater or lymph node (N+) disease or distant metastasis (M1), or an increase in grade from low to high per the IBCG recommendations.
- Disease-Free survival at 3, 6, 18, and 24 months from randomization. A patient is considered as disease-free at a timepoint if the disease has not recurred nor progressed, and the patient is still alive.
- Overall Disease free survival (DFS): DFS is the time from randomization until the day of disease recurrence or progression
- Overall survival (OS): OS is the time from randomization until the day of death by any cause or censoring
- Proportion of patients undergoing a repeat TURBT by 12 months and by 24 months from randomization
- Proportion of patients undergoing cystectomy by 12 months and by 24 months from randomization
- Immunological response (IR): Peripheral blood immunological response via intracellular cytokine staining (ICS) by ELISPOT of on CD8+ cells following HS-410 vaccination will also be evaluated

Phase 2 only:

- Safety of the combination of vesigenurtacel-L and BCG
- Safety of high dose vesigenurtacel-L monotherapy

Exploratory Endpoints

In patients completing at least 6 weekly doses of study medication, the following exploratory endpoints will be evaluated:

- Immunologic response of PBMCs (analysis of surface markers, CD3, CD4, CD8, degranulation) and stimulation analysis via ICS of IFN- γ , IL-2, TNF α and perforin.
- Total PBMC counts by flow cytometry, including lymphocyte subsets (B cells, helper T-cells, cytotoxic T-cells, NK cells and T-reg)

- Evaluation of tumour tissue obtained from pre-treatment resection for antigen expression by immunohistochemical analysis
- Evaluation of tumour tissue obtained from repeat biopsy, if clinically indicated, for presence of infiltrating T-lymphocytes
- T cell receptor sequencing of peripheral blood T cells before and during the course of treatment
- Immune cell infiltration and inflammatory cytokine levels in urine (phase 2 only)

Safety Endpoints

In both the phase 1 and 2 components of the study, safety assessments will include medical history, vital signs, physical exam, concomitant therapy and procedures, adverse events (AE) collection, serious adverse event (SAEs), clinical laboratory parameters, urinalysis and electrocardiograms (ECG).

3 Study Methods

3.1 General Study Design and Plan for Phase 1

The phase 1 component of the current protocol will evaluate the safety and tolerability of HS-410, administered at a weekly dose of 1×10^6 cells per 0.5 mL administration. Three patients will initially be enrolled to receive HS-410 weekly for 6 weeks after induction treatment with BCG. After a 1-week vaccine holiday for disease assessment, patients will receive HS-410 for an additional 6 weeks followed by 3 once monthly treatments for a total of 15 vaccinations. Patients will be observed weekly to assess the safety of HS-410. Dosing of the first 3 patients will be staggered by 2-week intervals to allow for safety evaluation before treating additional patients. If the DMC confirms HS-410 appears safe and well-tolerated in the 3 lead-in patients, dosing will be continued to 10 patients. The DMC will reconvene when all 10 patients in Phase 1 have received HS-410 and data is available for the Week 7 safety assessments from at least 6 patients. If this regimen is determined to be safe by the DMC, randomization to Phase 2 will commence.

3.2 General Study Design and Plan for Phase 2

[figure not shown]
Dosing in Phase 2 will begin when all 10 patients have been dosed in the Phase 1 cohort, at least 6 patients in that cohort have completed the Week 7 safety assessments, and the Data Monitoring Committee (DMC) has met to review this data and agreed it is safe to advance to Phase 2. A total of 100 patients will be assigned to four groups: 75 who will receive BCG will be randomized to arms combining either low dose vesigenurtacel-L (1×10^6 cells), high dose vesigenurtacel-L (1×10^7 cells), or placebo, respectively, with induction and maintenance BCG; 25 who will not receive BCG will be enrolled in the high dose vesigenurtacel-L monotherapy arm.

In the randomized arms, treatment will commence within 6 weeks of the most-recent TURBT or fulguration for patients with papillary disease and staging procedure for patients with CIS only. Patients will be treated during an induction phase with weekly intravesical BCG and intradermal blinded study product (vesigenurtacel-L or placebo) for 6 weeks followed by 6 weekly injections of blinded study product alone. During a subsequent maintenance phase, patients will receive an additional three courses of three once-weekly blinded study product injections in combination with intravesical BCG

approximately 3, 6, and 12 months after initiating induction BCG. Patients may receive additional courses of maintenance BCG in long-term follow-up at the investigator's discretion but should not receive any other cancer therapy prior to disease recurrence/progression (Figure 1).

In the monotherapy arm, treatment will commence within 6 weeks of the most-recent TURBT or fulguration for patients with papillary disease and staging procedure for patients with CIS only. Patients will be treated during an induction phase with weekly intradermal vesigenurtacel-L for 12 weeks. During a subsequent maintenance phase, patients will receive an additional three courses of three once-weekly vesigenurtacel-L injections approximately 3, 6, and 12 months after initiating induction vesigenurtacel-L.

Figure 1. Phase 1 and Phase 2 Study Design

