### 6.3 Long-term Follow-up Visits

All patients will be followed for the procedures listed below every 3 months from the date of the previous visit for 2 years then every 6 months from the date of the previous visit for a year or until study termination, whichever occurs first:

- Survival
- New anticancer treatments initiated after disease recurrence
- TURBT or fulguration procedures
- Cystectomy

In addition patients who have completed all study treatments or have discontinued study product dosing due to reason other than disease recurrence/progression will have the following procedures performed at each long-term follow-up visit:

- Cystoscopy/Cytology; biopsy if area suspicious for disease recurrence is identified at discretion of investigator (*Note: patients who have a biopsy performed will provide at least 4, non-stained, 10 micron sections for TCR sequencing and analysis of infiltrating T-cells.*) *If slides are not available, FFPE tissue (≥50 microns) is also acceptable.*

If a patient has recurrent/progressive disease and discontinues study treatment, the above disease assessment procedures will be discontinued, and subsequent long-term follow-up visits may be conducted via phone visit.

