##### **12.5.2.4 Overall disease-free survival**

Overall DFS is defined as the interval between the date of disease recurrence, progression, or death (whichever occurs first) and the date of randomization/treatment assignment (Arm 4) for patients without CIS. For patients with CIS at screening who have persistent disease at 6 months, the date of disease persistence will be defined as the date of randomization/treatment assignment (Arm 4) (i.e. DFS = zero).

Patients with CIS at screening who are disease-free by 6 months will have their overall DFS interval calculated between the date of disease recurrence, progression, or death (whichever occurs first) and the earliest date that the patient was determined to be disease-free. Patients will be censored at the last time of contact if recurrence, progression, or death has not been confirmed at the time of the analysis. Overall DFS will be analyzed using a log-rank test with a term for treatment assignment. In addition, Kaplan-Meier curves will be produced separately for each treatment group. The weighted log rank test will also be applied in an exploratory manner.

In a supporting analysis, a simple Cox proportional hazards model with treatment group as the sole independent variable will be built in order to estimate the hazard rate (HR) and 95%CI for overall DFS between the low and high dose vesigenurtacel-L groups relative to the control. A HR of less than one will provide initial evidence of a favorable outcome with vesigenurtacel-L. These analyses will be completed for the ITT and Per-Protocol populations.

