7.2 Secondary Efficacy Analyses

For time-to-event endpoints (e.g. DFS, OS), Kaplan-Meier / product limit method will be used to estimate the survival distributions over time, and to estimate median time to event. Where appropriate, inference for time-to-event endpoints will be assessed using the Log-rank test statistic, and the treatment effect will be estimated using Cox proportional hazards model. The assumption of proportional hazards will be assessed graphically.

The following will be analysed using Kaplan-Meier time-to-event methodology:

- Time To Recurrence, defined as the time from randomization to recurrence.
 - Recurrence is defined as disease that has recurred to the same extent of disease (ie same stage / severity) or to a lower stage/severity of disease compared to screening.
 - If recurrence has not occurred in a patient, the date of last disease assessment will be used as the timepoint for censoring.
 - The analysis will be repeated in an exploratory manner where recurrence is defined as only those recurrences to the same extent of disease (or greater) as screening.

- Time To Progression, defined as the time from randomization to progression.
 - Progression is defined as an increase in T stage from CIS or Ta (at screening) to T1 (lamina propria invasion), development of T2 or greater or lymph node (N+) disease or distant metastasis (M1), or an increase in grade from low to high per the IBCG recommendations..
 - If progression has not occurred in a patient, the date of last disease assessment will be used as the timepoint for censoring.

- Disease-Free Survival, defined as the time from randomization to recurrence or progression.
 - If a patient has recurred or progressed, then the first date the recurrence or progression has occurred will be used as the timepoint for the event.
 - If a patient has neither recurred nor progressed, then the date of last disease assessment will be used as the timepoint for censoring.

- Overall Survival, defined as the the time from randomization to death.
 - If a patient is still alive, then the patient will be censored on the date of most recent date known alive.
 - If a patient is lost to follow up, then the patient will be censored on the date last known alive.

- Time to cystectomy, defined as the time from randomization to cystectomy.
 - If a patient has not undergone cystectomy, the patient will be censored on the date of last disease assessment.

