- Burden of repeat TURBT, defined as the proportion of patients with no repeat TURBT vs 1 TURBT vs 2 TURBT vs 3 TURBT etc within 12 months since randomization (ie day 366 or earlier), within 18 months since randomization (ie day 548 or earlier) and within 24 months since randomization (ie day 731 or earlier).

For time to recurrence, time to progression, disease-free survival and overall survival, the Kaplan-Meier estimates on the proportion of patients free from the event of interest at 3, 6, 9, 12, 18 and 24 months from randomization will be presented.

For time to cystectomy, the Kaplan-Meier estimates on the proportion of patients with cystectomy at 12, 18 and 24 months from randomization will be presented. In addition, the time to cystectomy from original TURBT will be analysed in a similar way, and the data will be presented as sensitivity analysis.

For intensity of repeat TURBT, the same analysis will be repeated using the 12, 18 and 24 months since original TURBT, as sensitivity analysis.

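### One minus Kaplan-Meier overstates the proportion of patients with recurrence, because progression and death in effect censor recurrence

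*SAP*

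**What the plan says.** SAP 2.1 lists the proportion of patients with recurrence at five times from 3 to 24 months, "estimated based on Kaplan-Meier curves". Recurrence there means return of disease at the screening stage or lower, so progression is a separate event. The progression bullet in SAP 2.1 names no estimator, but SAP 7.2 puts both endpoints under Kaplan-Meier methods and reports "the Kaplan-Meier estimates on the proportion of patients free from the event of interest at 3, 6, 9, 12, 18 and 24 months" after randomization.

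The SAP 7.2 censoring rules are parallel:
- Recurrence: "If recurrence has not occurred in a patient, the date of last disease assessment will be used as the timepoint for censoring".
- Progression: "If progression has not occurred in a patient, the date of last disease assessment will be used as the timepoint for censoring".
- Time to cystectomy: also censored at the last disease assessment.

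No rule for these three endpoints says how death is handled, and neither document plans a cumulative-incidence method.

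The protocol determines who is still assessed. Section 7.2.1 makes progressive disease a mandatory reason to stop study treatment, whereas a patient with recurrence may continue if the investigator judges that best. Section 6.3 adds: "If a patient has recurrent/progressive disease and discontinues study treatment, the above disease assessment procedures will be discontinued". Section 3.1 also ends the cystoscopy schedule at progression.

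**The concern.** The endpoint is a proportion of patients. When some patients can no longer have the event, or can no longer be seen to have it, because something else came first, 1-KM does not estimate that proportion. It estimates what would happen if nobody progressed or died and the recurrence hazard stayed the same. The SAP never says that progression censors recurrence, but mandatory discontinuation, the end of assessments and censoring at the last assessment together produce that result. Death does the same.

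This matters because SAP 5.5 confines p-values to the primary comparison and presents secondary endpoints as point estimates with 95% confidence intervals. The point estimate is therefore the result that will be read. The bias grows with the event rate, so it does not cancel between arms even if both have the same mix of recurrence and progression.

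**Working it through.** **Plan figures.** The documents give no expected recurrence or progression proportion, so there is no figure of theirs to reproduce for these endpoints. The design rates used below are the ones behind the plan's power statement. One-sided Fisher's exact test at 0.10, with 23 evaluable patients per arm and 60% against 90%, has exact power 80.8%, which agrees with the stated 80%.

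**Inputs from the documents**
- One-year DFS: 60% in control and 90% in each experimental arm (Protocol 12.6.2).
- Disease assessment about every 3 months for 2 years (Protocol 10.1).

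**Assumptions not in the documents**
- The failure hazard is constant and carries on to 24 months.
- Progression is a share s = 10%, 25% or 50% of first failures, the same in every arm.
- There are no deaths in the main case, and 2% or 5% a year in the variant.

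**Formulas.** Let q be the failure probability per 3-month visit and k the number of visits.
- q = 1 - DFS^(1/4): 1 - 0.60^(1/4) = 0.1199 in control; 1 - 0.90^(1/4) = 0.0260 in an experimental arm.
- Recurrence per visit: r = (1 - s)q.
- 1-KM with progression censored: 1 - (1 - r)^k.
- Cumulative incidence: (1 - s)[1 - (1 - q)^k].

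**Example: control, s = 25%, 24 months (k = 8).** r = 0.75 × 0.1199 = 0.0899. 1-KM = 1 - 0.9101^8 = 52.9%. Cumulative incidence = 0.75 × (1 - 0.60²) = 0.75 × 0.64 = 48.0%. The excess is 4.9 points.

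**Control-arm recurrence, no deaths**

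| s | 12 mo: 1-KM / actual | Excess | 24 mo: 1-KM / actual | Excess |
|---|---|---|---|---|
| 10% | 36.7 / 36.0% | 0.7 | 59.9 / 57.6% | 2.3 |
| 25% | 31.4 / 30.0% | 1.4 | 52.9 / 48.0% | 4.9 |
| 50% | 21.9 / 20.0% | 1.9 | 39.0 / 32.0% | 7.0 |

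At the first visit (k = 1) both formulas equal r, so there is no excess.

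**Experimental arm at 90% one-year DFS.** At 12 months the excess is 0.1 point or less for every s. At 24 months it is:
- s = 10%: 17.25 - 17.10 = 0.15 point
- s = 25%: 14.57 - 14.25 = 0.32 point
- s = 50%: 9.94 - 9.50 = 0.44 point

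**Arm difference in recurrence at 24 months**

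| s | From 1-KM | Actual | Inflation |
|---|---|---|---|
| 10% | 42.6 | 40.5 | 2.1 points |
| 25% | 38.4 | 33.75 | 4.6 points |
| 50% | 29.1 | 22.5 | 6.6 points |

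**Deaths widen the gap.** In control with s = 25%, 1-KM at 24 months stays at 52.9%. The actual proportion falls to 47.1% with 2% deaths a year (excess 5.8 points) and to 45.7% with 5% (excess 7.2 points).

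**Progression behaves differently.** Simulated control arm, s = 25%, no deaths, any-time progression at 24 months:
- If all patients with recurrence are still assessed, 1-KM equals the actual proportion.
- If none is assessed further and their progression hazard triples, 1-KM gives 21.5% against an actual 30.9%.
- If the hazard is unchanged by recurrence, the actual proportion is 21.6%, but a cumulative incidence with recurrence as a competing event gives 16.0%, because it discards every progression after recurrence.

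**The case against.** The strongest reply is that the effect is small where it matters most and touches only secondary endpoints of a trial that SAP 5.5 calls exploratory. The primary endpoint uses Fisher's exact test, not Kaplan-Meier. At 12 months the control-arm excess is under half a patient in an arm of 25 (1.9% × 25 = 0.48), and the share of progression among first failures is assumed. All of this stands. It limits the weight of the point but does not make 1-KM the right estimator of a proportion, and at 24 months the distortion of the arm difference is no longer trivial.

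Two stronger readings are tempting, and the documents do not support either.

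First, a reader might infer that the progression proportion must be overstated too. Recurrence does not prevent later progression, SAP 7.2 does not censor progression at recurrence, and Protocol 7.2.1 lets patients with recurrence stay on treatment and under assessment. The endpoint is progression at any time, so the bias can be nil, upward (through deaths) or downward.

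Second, a reader might infer that the recurrence and progression proportions must add to more than the DFS failure rate. One patient can have both events, so an excess can be legitimate. At the first visit there is none (12.0% against 12.0% in control with no deaths). The answer also depends on which DFS definition is used. SAP 7.2 has "Disease-Free Survival, defined as the time from randomization to recurrence or progression", without death. The SAP 2.1 timepoint version requires that "the disease has not recurred nor progressed, and the patient is still alive", and Protocol 12.5.2.4 uses "the interval between the date of disease recurrence, progression, or death (whichever occurs first"). Once death counts, the order can reverse: in an experimental arm at 12 months the sum is 10.1-10.2% against 11.8% DFS failure with 2% deaths a year.

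**Conclusion.** The point holds for recurrence. The planned 1-KM does not estimate the stated proportion and overstates it once progressions or deaths have occurred at earlier visits. The 24-month arm difference is inflated by roughly 2 to 7 points in the vaccine's favour if the design's 60% and 90% rates hold. These sizes rest on constant hazards, 3-monthly visits, no deaths and an assumed 10-50% progression share common to the arms; deaths would enlarge the overstatement of recurrence.

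Time to cystectomy has the same problem in principle with death, and its size was not calculated. For progression the documents support only the statement that the target and the handling of death and of lost assessments are unstated, with the direction of bias unknown. This is a worthwhile, low-cost correction to secondary endpoints and does not threaten the primary analysis.

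**What to change.** In SAP 2.1 and 7.2:

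1. **Recurrence.** Report the proportions at each time by Aalen-Johansen cumulative incidence, with progression before recurrence and death as competing events.
2. **Cystectomy.** Report cumulative incidence with death as the competing event.
3. **Progression.** State that the target is progression at any time. Treat only death as competing; do not treat recurrence as competing. State that patients whose assessments stop after recurrence are censored there, and that the direction of the resulting bias is unknown.
4. **Cox models.** Keep the hazard ratios and label them cause-specific.

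Survival and cystectomy are already collected for all patients in long-term follow-up (Protocol 6.3). The change costs SAP wording and a standard procedure, with no new data and no change to the primary analysis.
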